7.7.3. Study Procedures

7.7.3.1. General Preparation

Once the subject's eligibility has been determined, the subject is enrolled in the study. Subject may be offered a snack (e.g., granola bar) and/or beverage (e.g., water, juice), which they can refuse. Subject may have a blanket placed on them and/or hot water bottles placed under their hands (per request of subject or staff).

Subject may be asked to clean (with skin preparation materials such as an alcohol pad) or shave the area of application of study-related devices to allow a more secured placement of sensor and/or mask to skin. Adhesives may also be used to secure sensors, masks, arterial and/or venous lines, or other study equipment.

During data collection, the subject will be seated and/or lying in supine position and will be instructed to refrain from excessive movement during the study  Standard noninvasive monitors will be placed on the subject when preparing for the study procedures and used for subject monitoring during study procedures. A minimum of one FDA-cleared pulse oximeter sensor will be placed on the subject for the subjects' safety. Other monitors may include FDA-cleared ECG and blood pressure cuff(s). Blood pressure may be obtained from arm cuffs, leg cuffs, finger cuffs, or equivalent devices. Blood pressure may be taken/recorded manually or automatically depending on the device used. For data collection purposes blood pressure measurements may be obtained in various ways. 

Oxygen tank pressure will be checked and may be noted before the gas delivery procedures begin for subject safety purposes. For subject's safety, various vital sign parameters (including but not limited to end-tidal and/or partial pressure of carbon dioxide and respiration rate) will be monitored throughout the gas delivery procedures; these may be noted at the beginning and end of the procedures. Other vital sign parameters (including but not limited to blood pressure and/or temperature) may be monitored and recorded throughout the study for subject safety or data collection purposes 

Blood samples will be labeled with a numerical sample ID. Unlike diagnostic lab samples, these labels do not have personal identifying information such as name or birthdate. After testing, blood samples will be discarded in the appropriate biohazard waste bins.

7.7.3.2. Sensor Placement and Sensor Data Collection

Masimo INVSENSOR00069 will be placed on at least one finger. Raw device data from the study devices/sensors may be collected and stored using data collection software. Outputs from other devices may also be recorded (e.g., SpO₂, PVi, Pi, pulse rate, temperature, blood pressure, ECG and capnography).

7.7.3.3. Blood Sampling Procedures

A qualified person will complete blood draws. These blood draws may occur at various points during the length of the study and may include qualifying blood samples, baseline blood samples before study procedures begin, and blood

samples after study procedures are complete to ensure the subject's wellbeing.

A set of blood samples of approximately 2 mL each will be drawn at selected time intervals throughout the study for laboratory analysis. The blood sample will be collected in vacutainer tubes or syringes for analysis by standard laboratory methods which may include co-oximetry and analysis by other point of care devices.

The total amount of blood drawn during study participation will not exceed 400 mL (which is less than the standard amount in a blood donation).

7.7.3.5. Desaturation Procedures

[figure not shown]
Upon indication that the subject is comfortable, a gas mixture will be administered through the mask/mouthpiece. The gas mixture may include varying proportions of oxygen, carbon dioxide, and nitrogen. The proportion of oxygen in this mixture will be decreased in a controlled manner to lower the subject's blood oxygen saturation. The lowest targeted value will be 70% oxygen saturation. Readings near 70% will be immediately verified by a pulse oximeter or by blood gas analyzer to ensure that levels are within the targeted oxygen saturation range and to minimize time that the subject may drop below the targeted range.

Study personnel will record their observations.

The study will end with a FiO₂ greater than or equal to room air (21%) to help the subject re-saturate after the procedure.

7.7.3.6. Ending Procedures

At the conclusion of the procedures, the sensors/devices, intravenous and arterial lines and monitoring equipment will be removed from the subject. A set of predischARGE vitals, such as heart rate and blood pressure, may be obtained and recorded on the case report form to ensure subject's wellbeing. Study staff may take final blood draws of approximately 2 mL, in addition to the blood draws in the procedure section above, to verify the subject's blood values are within normal ranges (e.g., pH, glucose, etc.).

After the study has ended subjects will be offered a snack (e.g., granola bar) and something to drink (e.g., water or juice). Subjects may be asked to consume the food and/or liquid prior to leaving the clinical lab area for their safety due to study procedures such as blood removal and line placement. Subjects will be encouraged to remain in the study area until they feel fit to leave and may be asked to wait in the clinical lab or lobby waiting area for approximately 20 minutes.

The subject will be allowed to leave after medical personnel determine it is safe to do so. Subjects will be given instructions on post care. All subjects will be instructed to contact the principal investigator and/or study staff in the event of any potential complication.

Subjects will be paid according to the compensation breakdown on the consent form. The total overall study time is approximately 180 minutes. If the total procedure time exceeds 180 minutes, subjects will be compensated for the extra time.

7.8. Monitoring Plan

A separate document for the study monitoring plan will be developed and followed to ensure subject safety and GCP compliance.

8. STATISTICAL DESIGN AND ANALYSIS

This is a validation study for the SpO₂ function of the Masimo INVSENSOR00069. The study targets one objective, to assess the accuracy of INVSENSOR00069's peripheral oxygen saturation (SpO₂) against contemporaneous measurement from arterial blood gas (ABG) analysis. A total of 18 subjects are needed to meet study objectives.

8.1. Sample size

To allow for assessment of SpO₂ function of INVSENSOR00069 across the two biological sexes of male and female and three skin pigmentation groups of light, medium, and dark, a total of six demographic subgroups will be studied.

8.1.1. Assumptions

- Independent observations (SpO₂-SaO₂) and the six subgroups are also independent of one another.
- Effect size of 1%, based on pulse oximetry reading resolution.
- 5% significance level and 80% power.

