8.1.2. Sample size

 This study will target a minimum of 18 subjects but may be modified based on actual numbers required to maintain adequate power for the study. Depending

on dropout rates, additional subjects may be enrolled to obtain sufficient representative data for factors such as sex, skin pigmentation, oxygen saturation, and other factors as required.

The final A_{RMS} analysis will utilize statistical methods to ensure performance statistics are calculated with comparable density over the range 70-100% SaO₂ and account for multiple samples per subject. Statistical analysis for each subgroup will be performed to show differences in biases among different subgroups.

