8.2.3. Exclusion Criteria

The following data exclusion criteria will be applied before statistical analysis.

Data will be excluded in the event:

- Either reference or test device does not provide data.
- Incomplete study or early termination, where the desaturation protocol could not be completed.
- Reference device malfunctions and/or provides inconsistent saturation values.
- Discontinuities and abrupt dropouts due to instruments recalibration or device failure.
- Low signal quality, e.g., due to noise or interference. Specifically, the INOP Indicators with <SpO₂ Labels> : Chk Sensor, Extd, Update, Interference, Low Perf, and Poor Signal will be used for data exclusion.
- Subject's oxygen saturation is unstable. This is determined using multiple (up to 5) consecutive blood draws, to be stable within 1% to 2% SaO₂ of neighboring draws (as obtained from a reference device) to include the measurement pair.
- Exclusion of subjects that do not have desaturation points in the lowest saturation bin (70-80%).
- Exclusion of data to statistically equalize samples per subject, and across the 70-100% saturation bins.

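### Section 8.1.1 bases its 80% power on independent SpO₂-SaO₂ observations, but each subject gives repeated pairs, and no visible adjustment covers the power statement or the subgroup bias comparison

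*Combined protocol and SAP*

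**What the plan says.** Section 8.1 sizes the study so that SpO₂ function can be assessed in six subgroups, two sexes by three pigmentation groups. Section 8.1.1 lists the assumptions: "Independent observations (SpO₂-SaO₂) and the six subgroups are also independent of one another", an effect size of 1% taken from the reading resolution, and "5% significance level and 80% power". Sections 8 and 8.1.2 give 18 subjects, in 8.1.2 as a minimum that may be changed to keep power adequate.

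Other sections describe repeated measurement within a subject:

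- Section 7.7.3.3: "A set of blood samples of approximately 2 mL each will be drawn at selected time intervals throughout the study for laboratory analysis".
- Section 8.2.3, on judging whether saturation is stable: "This is determined using multiple (up to 5) consecutive blood draws".
- Section 8.2.3 also plans "Exclusion of data to statistically equalize samples per subject, and across the 70-100% saturation bins".
- Section 8.1.2 says the final A_RMS analysis will "account for multiple samples per subject", and 8.2.1 says the A_RMS will be adjusted for repeated measurements.

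The next sentence of 8.1.2 is "Statistical analysis for each subgroup will be performed to show differences in biases among different subgroups". It mentions no adjustment. In 8.2.1, Bias and Precision are plain formulas over n pairs. The only acceptance criterion, in 8.2.2, is overall A_RMS of at most 2%.

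**The concern.** The formulas in 8.2.1 sum the difference SpO₂ minus SaO₂ over individual pairs. The same expression qualifies the word *observations* in 8.1.1, so the natural reading is that pairs are assumed independent. Pairs from one subject share that subject's finger, skin and physiology, and the plan itself recognises this when it adjusts the A_RMS.

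Two things are at stake. First, the 80% would describe a design with more independent information than this one has. Second, a comparison of bias between pigmentation or sex groups that counts pairs as independent would look more precise than it is, and could suggest subgroup differences that are only differences between a few subjects. The Bias point estimate is not at issue: with equal samples per subject, correlation changes its standard error and not its value.

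**Working it through.** **The plan's own figure.** The 18 can be neither reproduced nor refuted. The visible text gives no SD, correlation, number of pairs, test or sidedness, and the start of 8.1.2 is blank in the public copy. As one reference point, suppose there is one summary per subject and a one-sample test of an overall bias of 1% (two-sided 5%, 80% power). By the normal approximation, 18 subjects suffice if the SD of the summaries is at most √18/(1.96 + 0.8416) = 1.51. By the t-test with 17 df the limit is 1.43. On that reading 18 may well be adequate.

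**Inputs.** From the plan: 18 subjects, six subgroups, 1% effect, 5% level (8, 8.1, 8.1.1). Assumed: equal allocation (18/6 = 3 per subgroup), two-sided testing, pair SD 1.5%, m = 21 pairs per subject, and intraclass correlation (ICC) 0, 0.05 or 0.1.

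**Standard error.** Treating m pairs per subject as independent understates the standard error of a subgroup bias by √(1 + (m − 1)·ICC).

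- m = 21, ICC 0.05: √(1 + 20 × 0.05) = √2 = 1.41.
- m = 21, ICC 0.1: √(1 + 20 × 0.1) = √3 = 1.73.
- m = 15 to 30: 1.30 to 1.57 at ICC 0.05, and 1.55 to 1.97 at ICC 0.1.

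A z-test that treated 20 pairs per subject as independent at ICC 0.1 would have a ratio of √2.9 = 1.70. Its true type I error would be P(|Z| > 1.96/1.70), about 0.25 against a nominal 0.05.

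**Power.** The SD of a subject mean is s = SD·√(ICC + (1 − ICC)/m), which gives 0.327, 0.463 and 0.567 at ICC 0, 0.05 and 0.1. The noncentrality for a 1% difference with k subjects per group is 1/(s·√(2/k)). Noncentral t, with 12 df (18 subjects minus 6 subgroups):

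| Contrast | ICC 0 | ICC 0.05 | ICC 0.1 |
|---|---|---|---|
| 3 v 3 subjects | 93% | 68% | 51% |
| 6 v 6 | 99.8% | 93% | 80% |
| 9 v 9 | 100% | 99% | 93% |

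For 3 v 3, a stand-alone two-group test (4 df) gives 80%, 52% and 38%. With pair-level df, the ICC 0 figure is about 96%. At SD 1.0 and ICC 0.1, 3 v 3 still has 84% with 12 df.

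**Would more draws cure it?** Section 7.7.3.3 says "The total amount of blood drawn during study participation will not exceed 400 mL". At about 2 mL each, that is at most 400/2 = 200 draws. With m = 200, SD 1.5 and ICC 0.1, s = 0.485 and 3 v 3 power is 64% (12 df). More draws help a little but do not remove the effect.

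**Would equalizing samples cure it?** No. It balances the weight of each subject and leaves the correlation within subjects in place.

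**The case against.** The strongest reply is the redaction. The blank at the start of 8.1.2 is where the calculation would stand, and it may give the contrast, SD, unit and number of pairs. That stands: a reader might infer that the sample size was never justified, and the public text does not support that.

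Second, the sentence in 8.1.2 about multiple samples speaks of performance statistics, which could include Bias and Precision. A reader might infer that the plan ignores clustering everywhere except in A_RMS, and that is too strong. But the sentence is about the final A_RMS analysis, and the subgroup sentence that follows carries no such provision.

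Third, *observations* could mean one summary per subject, in which case the assumption can hold. This is possible, but the text does not say so and the notation in 8.2.1 points the other way.

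Fourth, no subgroup interval, test or criterion is promised. The subgroup comparison may be purely descriptive, so an interval that is too narrow remains a conditional harm. The sole acceptance criterion already has its own adjustment. Both points stand and limit the consequence.

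Last, the power figures rest on assumed inputs and fall below 80% in some settings and not in others. A reader might infer from the 3 v 3 row that 18 subjects are too few. The documents do not support that, since they do not say in the visible text that the 1% refers to a difference between single subgroups.

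**Conclusion.** The point holds in a limited form. Section 8.1.1 states an assumption that, on its natural reading, the design does not meet, and no visible text carries the repeated-measures adjustment over to the power statement or the subgroup bias comparison. The direction is certain for any positive within-subject correlation: lower power than under independent pairs, and subgroup standard errors that are too small if pairs are counted as independent. The size is not known. The factors of 1.4 and 1.7 rest on an assumed 21 pairs per subject and ICCs of 0.05 and 0.1; the power figures also rest on the assumed SD, contrast, allocation and degrees of freedom.

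No shortfall in the 18 subjects is shown, and the overall A_RMS criterion of at most 2% is unaffected. Severity is minor to should-fix.

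**What to change.** 1. In 8.1.1, replace the independence assumption for observations with a statement that subjects are independent and pairs within a subject are correlated. If one summary per subject was meant, say that instead.
2. In 8.1.2, state that subgroup bias differences, and any intervals or tests on them, use the subject as the cluster, through subject means or a mixed model with a random subject effect.
3. If the withheld calculation in 8.1.2 treated pairs as independent, restate the power or the minimum detectable difference at subject level, and give the lower figure where 80% is not reached. If it already uses the subject as the unit, only the wording of 8.1.1 needs aligning.

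The existing provision to modify the minimum of 18 can stay. The cost is a wording change and minor analysis work, with no added subjects. The downside is wider subgroup bias intervals and possibly a less favourable stated power.

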8.1.2. Sample size

 This study will target a minimum of 18 subjects but may be modified based on actual numbers required to maintain adequate power for the study. Depending

on dropout rates, additional subjects may be enrolled to obtain sufficient representative data for factors such as sex, skin pigmentation, oxygen saturation, and other factors as required.

The final A_{RMS} analysis will utilize statistical methods to ensure performance statistics are calculated with comparable density over the range 70-100% SaO₂ and account for multiple samples per subject. Statistical analysis for each subgroup will be performed to show differences in biases among different subgroups.

8.2. Data Analysis

8.2.1. Accuracy Calculations

Accuracy will be reported as the Bias, Precision, and A_{RMS} using the following equations:

$$Bias = \frac{1}{n} \sum_{i=1}^n (SpO_{2i} - SaO_{2i})$$

$$Precision = \sqrt{\frac{\sum_{i=1}^n (SpO_{2i} - SaO_{2i} - Bias)^2}{n - 1}}$$

$$A_{RMS} = \sqrt{\frac{\sum_{i=1}^n (SpO_{2i} - SaO_{2i})^2}{n}}$$

The A_{RMS} will be adjusted to account for repeated measurements on each subject.

8.2.2. Acceptance Criteria

- SpO₂: A_{RMS} ≤ 2% over the range 70-100%, under no motion.

8.2.3. Exclusion Criteria

The following data exclusion criteria will be applied before statistical analysis.

Data will be excluded in the event:

- Either reference or test device does not provide data.
- Incomplete study or early termination, where the desaturation protocol could not be completed.
- Reference device malfunctions and/or provides inconsistent saturation values.
- Discontinuities and abrupt dropouts due to instruments recalibration or device failure.
- Low signal quality, e.g., due to noise or interference. Specifically, the INOP Indicators with <SpO₂ Labels> : Chk Sensor, Extd, Update, Interference, Low Perf, and Poor Signal will be used for data exclusion.
- Subject's oxygen saturation is unstable. This is determined using multiple (up to 5) consecutive blood draws, to be stable within 1% to 2% SaO₂ of neighboring draws (as obtained from a reference device) to include the measurement pair.
- Exclusion of subjects that do not have desaturation points in the lowest saturation bin (70-80%).
- Exclusion of data to statistically equalize samples per subject, and across the 70-100% saturation bins.

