15.4. Device Deficiencies Reporting

All Masimo device related deficiencies should be reported to the sponsor and must be recorded in the CRF in a timely manner. When a Masimo device deficiency is observed, every effort should be made to return the device and its packaging to the sponsor in a timely manner.

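### The exclusion for discontinuities caused by device failure does not say which device, so displayed, unflagged SpO₂ readings of the product under test can be removed before A_RMS is judged against 2%

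*Combined protocol and SAP*

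**What the plan says.** Section 8.2.2 sets one acceptance criterion: "A_{RMS} ≤ 2% over the range 70-100%, under no motion". It is applied to a point value; no confidence bound is stated there.

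Section 8.2.3 lists the data exclusions and fixes their timing: "The following data exclusion criteria will be applied before statistical analysis". Four of its bullets matter here:

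- No value: "Either reference or test device does not provide data".
- Reference faults: "Reference device malfunctions and/or provides inconsistent saturation values".
- Flagged test readings: "Chk Sensor, Extd, Update, Interference, Low Perf, and Poor Signal will be used for data exclusion".
- The bullet at issue: "Discontinuities and abrupt dropouts due to instruments recalibration or device failure".

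The only adjustments to A_RMS in the readable text of section 8 concern repeated measurements (section 8.2.1: "The A_{RMS} will be adjusted to account for repeated measurements on each subject") and comparable density of data over the saturation range (section 8.1.2). Neither concerns excluded pairs.

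Separately, section 15.4 requires that "All Masimo device related deficiencies should be reported to the sponsor and must be recorded in the CRF in a timely manner". It does not refer to the exclusions in section 8.2.3.

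**The concern.** The no-value and reference-fault bullets say which device they mean. The bullet on discontinuities does not, so on its ordinary reading it includes the product being validated. It also gives no size of jump, no evidence needed to attribute a jump to failure, no decision-maker, and no requirement that this person be unaware of the SpO₂–SaO₂ difference.

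In an accuracy validation, a wrong value shown by the test device with no warning is an error of the product. A flagged reading is different, because there the device itself tells the user not to rely on it. If unflagged failure readings can be set aside after the fact, the single 2% verdict may describe the device with some of its failures removed. The readable text plans no A_RMS with those pairs restored and no count of exclusions by reason.

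**Working it through.** **What the bullet can reach.** Setting the section 8.2.3 bullets beside the equipment described in sections 7.5 and 7.7.3.2:

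| Event | Other bullet that covers it | Reached by the discontinuity bullet | Effect on A_RMS of removal |
|---|---|---|---|
| Either device shows no value | Yes | Yes (dropout) | None; there is no difference to square |
| Reference analyser fault | Yes | Yes | Removes a reference error, not a product error |
| Recalibration gap or jump | Only if no value results or the reference is at fault | Yes | Not a product error if it arises in the reference or recording equipment |
| Recording-equipment fault | Only if no value results | Yes | Not a product error |
| Test device displays a jump with one of the six flags | Yes | Yes | Removed in any case |
| Test device displays a jump with no listed flag, attributed to its failure | None specific to it | Yes, as worded | Removes a product error |

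Only the last row is in dispute.

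**Direction.** By the section 8.2.1 formula, A_RMS² is the mean of the squared differences. Removing a pair lowers A_RMS exactly when its absolute difference exceeds the A_RMS of the set that contains it. An abrupt failure reading will usually meet that condition, though not always.

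**Size.** The plan has no figure to reproduce here: 2% is a criterion, and the number of pairs is not given in the readable text. Let n be all pairs, k the pairs removed as failure readings, e their absolute error, and b the A_RMS of the rest. Then

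A_RMS² = [(n − k)b² + k·e²] / n,

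and the smallest k that gives A_RMS > 2 is floor[n(4 − b²)/(e² − b²)] + 1.

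Assumptions not in the documents: n = 360 (18 subjects × 20 pairs), e = 10 points, b = 1.5 to 1.9.

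- b = 1.9: 360 × 0.39 / 96.39 = 1.46, so k = 2 (0.6% of pairs). With them, √[(358 × 3.61 + 200)/360] = 2.036; without them, 1.9.
- b = 1.7: 360 × 1.11 / 97.11 = 4.11, so k = 5 (1.4%). With them, √[(355 × 2.89 + 500)/360] = 2.059; without them, 1.7.
- b = 1.5: 360 × 1.75 / 97.75 = 6.45, so k = 7 (1.9%). With them, √[(353 × 2.25 + 700)/360] = 2.037; without them, 1.5.

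**Range.** Pairs needed, by assumption:

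| n | e | b = 1.5 | b = 1.7 | b = 1.9 |
|---|---|---|---|---|
| 180 | 10 | 4 | 3 | 1 |
| 450 | 10 | 9 | 6 | 2 |
| 360 | 5 | 28 | 19 | 7 |
| 360 | 8 | 11 | 7 | 3 |
| 360 | 15 | 3 | 2 | 1 |

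If 1% of pairs are off by 10 points, A_RMS on all pairs is 1.80, 1.96 or 2.14 for b = 1.5, 1.7 or 1.9, so only the last case changes the verdict.

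**The case against.** The strongest reply is that the bullet has a legitimate use and that the disputed case is narrow. Several parts of this stand.

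- A reader might infer that, recalibration aside, the bullet adds only unflagged errors of the test device. The documents do not support that. The bullets overlap, and section 7.5 lists data-collection equipment separately from the test device and the comparators. A recording fault is a natural target of this bullet.
- A reader might also infer that the removed pairs are large errors by definition. They are not. The bullet is conditioned on cause, not on the SpO₂–SaO₂ difference, and a dropout with no value adds nothing.
- To matter, a reading must be displayed, show a jump, carry none of six flags, be attributed to failure, and coincide with an otherwise eligible blood draw. Nothing in the documents says how often this happens. Smooth bias or an ordinary wrong reading is outside the bullet unless someone labels it a failure.
- A test-unit failure should leave a trace. Section 15.1 counts malfunctions and inadequate performance as device deficiencies, section 15.4 requires them in the CRF, and under section 9.3 the monitor checks CRF entries.

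These points narrow the concern without removing it. The deficiency record does not return a pair to A_RMS and is not tied to the exclusions. Rarity is no safeguard, because with large errors few pairs are needed. If only reference or recording faults were meant, saying so costs almost nothing.

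**Conclusion.** As worded, section 8.2.3 permits displayed, unflagged SpO₂ values of INVSENSOR00069 to be removed before the acceptance decision when they are attributed to a failure of that device. No readable part of the plan restores or counts them. Removal would usually favour passing. On the stated assumptions, between 2 and 7 pairs in 360 with 10-point errors would separate a pass from a fail; with 5-point errors it takes 7 to 28.

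This is a statement about what the rule allows. It does not support the stronger reading that the 2% criterion will be met by deletion, or that this is the bullet's purpose. The number and size of such readings are unknown, and with none of them the result is unchanged. The arithmetic uses the unadjusted formula. The effect after adjustment for repeated measurements and equalisation across subjects and saturation bins was not computed. Part of section 8.1.2 appears to be blacked out, so the absence of a safeguard is a statement about the readable text. The point merits a cheap correction and does not call the design into question.

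**What to change.** In section 8.2.3, limit the bullet to recalibration or failure of the reference analyser or the data-recording equipment. Add that an SpO₂ value displayed by INVSENSOR00069 without one of the six listed flags may not be removed under this bullet because of test-device failure. State that the other exclusions in section 8.2.3 still apply, so that the sentence does not override the rules on instability, reference faults, the lowest saturation bin or equalisation.

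If a hardware fault of a test unit is documented under section 15.4, keep its pairs in the primary A_RMS. Report A_RMS without them as a sensitivity result, and give the number of affected pairs by subject and pigmentation group.

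The cost is a short wording change and, only if a fault occurs, one extra A_RMS calculation and a count. The drawback for the sponsor is that the primary A_RMS may be slightly less favourable. A unit that was genuinely broken can still be shown to be the cause through the sensitivity result.

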9. DATA MANAGEMENT

9.1. Data Management and Confidentiality

All documents associated with this protocol will be securely stored in a physical location or on password-protected computers. The confidentiality and retention of these documents will be protected to the extent provided and required by the law. All data will be de-identified before any statistical analysis. Only de-identified data will be shared with Masimo for research purposes stated in this protocol. Data collected by the eCRF data capture software will be shared with Masimo via a secure, password-protected server that only study staff and Masimo study team members will have access to. Data will be retained for a minimum of two years following completion of the final analysis.

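### Does the 1% to 2% SaO₂ stability range in section 8.2.3 leave the A_RMS verdict open?

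*Combined protocol and SAP*

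**What the plan says.** Section 8.2.3 opens with "The following data exclusion criteria will be applied before statistical analysis". One entry in its list concerns unstable saturation: "This is determined using multiple (up to 5) consecutive blood draws, to be stable within 1% to 2% SaO₂ of neighboring draws", with SaO₂ "as obtained from a reference device) to include the measurement pair". A separate entry removes data when "Reference device malfunctions and/or provides inconsistent saturation values". Later entries remove subjects with no points in the lowest bin (70-80%) and equalize samples per subject and across saturation bins.

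Section 8.2.2 has one acceptance criterion: A_RMS of at most 2% "over the range 70-100%, under no motion". Section 8.2.1 gives the A_RMS formula and says it will be adjusted for repeated measurements. Section 8 sets the sample at 18 subjects.

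No readable section narrows the range to one limit or defines a neighbouring draw. The figure in section 7.7.3.5 and the content of Appendix II (the desaturation schedule) are not visible in the public file, so the draw pattern may be described there.

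**The concern.** A rule that decides which pairs enter the only acceptance test should normally point to one set of pairs. Here the limit could be 1%, 2% or something between. The comparison could be with the previous draw, with both adjacent draws, or with every draw in the set. If pairs taken while saturation is moving carry larger errors (for example because SpO₂ lags SaO₂), the stricter limit gives a lower A_RMS. A device near 2% might then pass under one reading and fail under another.

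There is also a question of timing. No readable text says who applies the list, or that this person cannot see SpO₂. Section 9.1 says "All data will be de-identified before any statistical analysis", but that protects identity and does not hide device readings. If the limit were picked after the errors had been seen, the pass rate of a device that should fail would rise.

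**Working it through.** The plan has no calculated figure to reproduce here, since 2% is a criterion. The check asks how far the choice of limit can move the result.

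**Inputs.** From the plan: limits of 1% and 2% and up to 5 draws (8.2.3), 18 subjects (8), pass if A_RMS ≤ 2% (8.2.2). Assumed, because the documents are silent: 5 plateaus of 5 draws; SaO₂ moving as a random walk with step SD *d* per draw; subject bias SD 1%; SpO₂ lag of 0 or half a draw interval; a pair kept if both adjacent steps are within the limit (one step for end draws). A_RMS is pooled, without the repeated-measures adjustment or the equalization, whose methods are not stated.

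**Step 1: what the rule uses.** Only SaO₂ from the reference device. Neither SpO₂ nor the difference SpO₂ − SaO₂ enters, so the rule does not select on device error directly.

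**Step 2: share of pairs kept.** With limit *L*, one step passes with probability p = 2Φ(L/d) − 1. Of five draws, two are ends and three are interior, so the share kept is (2p + 3p²)/5. For d = 1% and L = 1%, p = 0.683 and the share is (1.365 + 1.398)/5 = 0.55. For L = 2%, p = 0.954 and the share is (1.909 + 2.733)/5 = 0.93.

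| Drift SD per draw | Kept at 1% | Kept at 2% |
|---|---|---|
| 0.3% | 99.9% | 100% |
| 0.5% | 93% | 100% |
| 0.75% | 73% | 99% |
| 1.0% | 55% | 93% |
| 1.5% | 35% | 73% |

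The limits differ materially only when drift is about 0.5% per draw or more.

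**Step 3: when A_RMS moves.** Let A₁ be A_RMS at the 1% limit, f the share of the pairs kept at 2% that the 1% limit would drop, and r the RMS error of those extra pairs. Then A₂² = (1 − f)A₁² + f r². If r = A₁, A₂ = A₁. For A₂ to exceed 2%, r must exceed √[(4 − (1 − f)A₁²)/f]. With d = 1%, f = (0.93 − 0.55)/0.93, about 0.40:
- A₁ = 1.90%: r > √[(4 − 0.6 × 3.61)/0.4] = 2.14%
- A₁ = 1.80%: r > √[(4 − 0.6 × 3.24)/0.4] = 2.27%
- A₁ = 1.70%: r > √[(4 − 0.6 × 2.89)/0.4] = 2.38%

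With f = 0.20 the thresholds rise to 2.36%, 2.65% and 2.91%.

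**Step 4: opposite verdicts.** Simulated studies (2,000 to 4,000 per case) with the residual SD set so that A_RMS over all pairs equals the stated value; ranges cover lag 0 and 0.5.

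| Drift SD | All-pairs A_RMS | Opposite verdicts, 1% v 2% limit |
|---|---|---|
| 1.0% | 1.5% | 0% |
| 1.0% | 1.7% | at most about 1% |
| 1.0% | 1.8% | 3-4% |
| 1.0% | 2.0% | 15-16% |
| 1.0% | 2.1% | 11-17% |
| 1.0% | 2.3% | about 1% or less |
| 0.75-1.5% | 2.0% | 11-21% |
| 0.5% | 2.0% | 5-6% |
| 0.3% | 2.0% | under 1% |

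With no lag, mean A_RMS is the same under both limits, and disagreements are chance differences at the cut-off (median gap about 0.04 percentage points at d = 1%). With lag, at all-pairs A_RMS 1.8%, the means are 1.76% and 1.78%.

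**Step 5: picking the limit afterwards.** At d = 1% and all-pairs A_RMS 2.1%:

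| Limit used | Pass rate, no lag | Pass rate, lag 0.5 |
|---|---|---|
| 2%, fixed in advance | 17% | 21% |
| 1%, fixed in advance | 21% | 31% |
| Better of the two | 25% | 35% |

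Picking afterwards adds 4 points over the fixed 1% limit in both columns, and 8 and 14 points over the fixed 2% limit.

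**The case for a change.** The best case for a change is that the range is real, feeds the only verdict and would cost almost nothing to close. Take assumed draws of 80.0, 81.2, 82.6, 83.1 and 83.3. The 1% limit keeps three pairs (previous draw), two (both adjacent), three (either adjacent) or none (whole set). The 2% limit keeps five, five, five or none.

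Harsher assumptions also give larger effects. With 6 plateaus of 5 draws, drift SD 1% and a lag of a full draw, mean A_RMS was 1.84% at the 1% limit and 1.96% at the 2% limit. Pass rates were 93% and 68%, and verdicts differed in about 25% of studies. Across eight combinations of limit and neighbour rule, some pair of readings disagreed in about 50%.

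The arithmetic stands, and so does the point that the readable text does not fix one set of pairs. Its weight is limited in three ways. These cases need strong drift, a long lag and A_RMS just under 2% together, and the documents give no reason to expect that. With A_RMS of about 1.5% to 1.65%, the eight readings disagreed in under 1% of studies. The spread also includes a whole-set comparison that keeps only about one pair in ten at the 1% limit, which is a strained reading of neighbouring when the draws are described as consecutive.

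The lack of a named masked person adds little. Stability is read from analyzer values, and the limit has to be settled for the list to be applied before the analysis, as 8.2.3 requires. Picking the better limit later would depart from that. Inconsistent reference values most naturally means inconsistent among reference readings, so that entry shows no separate fault.

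**Conclusion.** No change follows. The range is a gap in detail that an analyst can fill sensibly: choose a limit within 1% to 2%, compare adjacent draws, and apply this to SaO₂ before computing A_RMS. Either end follows the plan and gives a sound accuracy estimate under stable saturation, and nothing in the documents makes one end better than the other.

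The verdict is sensitive only in a narrow band. At drift SD 1%, opposite verdicts peak at about 15% to 17% with all-pairs A_RMS of 2.0% to 2.1%, and fall to about 1% or less at 1.7% and at 2.3%. At A_RMS 2.0%, they fall to 5% to 6% with drift SD 0.5% and under 1% with 0.3%.

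These sizes rest on assumed drift, lag, subject bias and plateau structure, and on a pooled A_RMS. The unmodelled equalization and repeated-measures adjustment could shift them either way. The conclusion itself rests on two things the plan does state: stability is judged on reference SaO₂, and exclusions come before the analysis.
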